9.2.1 Primary Efficacy Analysis

The primary endpoint (at Week 12) is ACR20 response at Week 12. Analysis of the primary endpoint will be conducted on the FAS based on randomized treatment groups (Upadacitinib 7.5 mg QD, Upadacitinib 15 mg QD, Upadacitinib 30 mg QD and the combined placebo groups). Point estimate and 95% CI using normal approximation will be provided for the response rate for each randomized treatment group. The dose-response curve will be shown graphically with CI for each dose. Cochran-Armitage test will be conducted for demonstrating non-flat dose response relationship.

Comparisons of the primary endpoint will be made between each Upadacitinib dose and the combined placebo group using the Cochran-Mantel-Haenszel test adjusting for stratification factor prior bMDARD use. Point estimate, 95% CI using normal approximation and p-value for the treatment comparison will be presented. For the primary analysis, non-responder imputation (NRI) will be used.

9.2.2 Sensitivity Analysis of Primary Efficacy Variables

The primary analysis for point estimate and CI will be repeated using OC as a sensitivity analysis. This will be conducted on the FAS based on randomized treatment groups.

Supportive NRI analysis will also be conducted on the Per Protocol Analysis Set.

9.2.3 Key Secondary Efficacy Analyses

Key secondary endpoints at Week 12 are:

1. Change from baseline in DAS28 (CRP);
2. Change from baseline in HAQ-DI;
3. ACR50 response rate;
4. ACR70 response rate;
5. Change from baseline in Short Form-36 (SF-36) Physical Component Score (PCS);
6. Proportion of subjects achieving LDA based on DAS28 (CRP);
7. Proportion of subjects achieving Clinical remission (CR) based on DAS28 (CRP);
8. ACR20 response rate of Week 1;
9. Change from baseline in Functional Assessment of Chronic Illness Therapy-Fatigue (FACIT-F);
10. Change from baseline in Work Instability Scale for Rheumatoid Arthritis (RA-WIS);
11. Change from baseline in morning stiffness (severity).

For binary endpoints, frequencies and percentages will be reported for each randomized treatment group. Similar analyses as for the primary endpoint will be conducted.

For the major RA continuous endpoints DAS28 and HAQ-DI change from baseline, statistical inference will be conducted using analysis of covariance (ANCOVA) coupled

with MI for missing data handling. Specifically, the ANCOVA model will include treatment as the fixed factor, and the corresponding baseline value and the stratification factor prior bDMARD use (Yes/No) as the covariates. For other continuous endpoints, statistical inference will be conducted using the MMRM model as described in Section 9.1.2, with the main stratification factor being prior bDMARD use (Yes/No). From both the MI and MMRM analyses, the LS mean and 95% CI will be reported for each randomized treatment group; the LS mean treatment difference and associated 95% CI and p-value will be reported comparing each Upadacitinib dose group with the combined placebo group.

9.2.4 Exploratory Efficacy Analyses

Additional efficacy analysis includes the following endpoints at all visits in Period 1:

- Change from baseline in individual components of ACR response;
- ACR20/50/70 response rates;
- Change from baseline in DAS28 (CRP) and DAS28 (erythrocyte sedimentation rate [ESR]);
- Change from baseline in morning stiffness (severity and duration);
- Proportion of subjects achieving LDA and proportion of subjects achieving CR based on DAS28 (CRP), DAS28 (ESR), Simplified Disease Activity Index (SDAI), and CDAI criteria;
- Change from baseline in EQ-5D-5L;
- Change from baseline in SF-36.
- Change from baseline in FACIT-F
- Change from baseline in RA-WIS

For binary endpoints, point estimate and 95% CI using normal approximation will be provided for the response rate for each randomized treatment group. Point estimate, 95% CI and p-value will be provided for the treatment comparison between each Upadacitinib dose group and the combined placebo group using the Cochran-Mantel-Haenszel test adjusting for stratification factor prior bDMARD use. The 95% CI will be based on

normal approximation. NRI will be used as primary analysis and OC will be used as sensitivity analysis.

For continuous endpoints, the LS mean and 95% CI will be reported for each randomized treatment group. The LS mean treatment difference and associated 95% CI and p-values between each Upadacitinib dose group and the combined placebo group will be provided using MMRM model with fixed effects of treatment, visit and treatment-by-visit interaction, prior bDMARD use and baseline value as covariate.

9.2.5 Handling of Multiplicity

Multiplicity on the primary endpoint is controlled via using the Cochran-Armitage test across the multiple doses. Nominal pairwise comparison of each Upadacitinib dose to placebo is also performed as supportive information.

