**Key Secondary Efficacy Analysis:**

The key secondary efficacy endpoints (at Week 12) will be evaluated. For a list of the key secondary endpoints, see "Efficacy" part in "Criteria for Evaluation."

All nominal statistical comparisons of upadacitinib versus placebo for the primary and key secondary endpoints and for the three doses will be conducted using a two-sided significance level of 0.05.

For the analysis of binary endpoints, frequencies and percentages will be reported for each treatment group. Pairwise comparisons between each upadacitinib group and the combined placebo groups will be conducted using the Cochran-Mantel-Haenszel test adjusting for main stratification factors.

For continuous endpoints, the mean, standard deviation, median, and range will be reported for each treatment group. Pairwise comparisons between each of the upadacitinib treatment groups and the combined placebo groups will be carried out using the analysis of covariance model with treatment group as the fixed factor, and the corresponding baseline value and the main stratification factors as the covariates.

Non-responder imputation approach will serve as the primary analysis approach for key binary endpoints, and multiple imputation will serve as the primary analysis approach for key continuous endpoints.

Sensitivity analyses based on observed cases will also be conducted for key endpoints.

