**5.6****Discussion and Justification of Study Design****5.6.1****Discussion of Study Design and Choice of Control Groups**

This study includes two periods.

Period 1 is a 12 week, randomized, double-blind, placebo-controlled period to confirm dose response in the efficacy of upadacitinib 7.5 mg QD and 15 mg QD and 30 mg QD, and to compare the safety and efficacy of upadacitinib versus placebo in subjects with moderately to severely active RA who are on a stable dose of csDMARDs and have an inadequate response to csDMARDs. Period 1 is designed to test superiority of

upadacitinib versus placebo for achieving the primary endpoint (ACR20) at Week 12, and other secondary efficacy parameters, all on a stable csDMARD therapy.

The purpose of Period 2 is to evaluate the long-term safety, tolerability, and efficacy of upadacitinib 7.5 mg QD, 15 mg QD and 30 mg QD in a blinded fashion in subjects with RA who have completed Period 1. Subjects who are assigned to upadacitinib treatment groups in Period 1 will continue to receive upadacitinib 7.5 mg QD, 15 mg QD and 30 mg QD per original randomization assignment in a blinded manner. Subjects who are assigned to placebo in Period 1 will be switched to receive upadacitinib 7.5 mg QD, 15 mg QD or 30 mg QD in a blinded fashion per pre-specified randomization assignments. Preventing dose reduction or escalation of upadacitinib during Period 2 will allow better assessments of long-term safety and efficacy of upadacitinib 7.5 mg QD, 15 mg QD versus 30 mg QD.

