#### **8.1.4.1.4      Multiplicity Control for the Primary and Key Secondary Endpoints**

Multiplicity on the primary endpoint is controlled via using the Cochran-Armitage test across the multiple doses. Nominal pairwise comparison of each upadacitinib dose to placebo is also performed as supportive information.

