## 8.2 Determination of Sample Size

Sample size was estimated based on the previous global Phase 2 trial (Study M13-537). Assuming an ACR20 response rate of 46% for placebo group, 62% for low dose group (7.5 mg QD), 68% for middle dose group (15 mg QD) and 80% for high dose group (30 mg QD) of upadacitinib, the sample size to have 90% power and two-sided alpha of 5% to detect a statistically significant dose-response using Cochran-Armitage test will be 42 subjects per group. And the sample size to demonstrate the superiority of upadacitinib compared to placebo will be 46 subjects to provide the 90% power and 5% of two-sided alpha. Taking 5% of drop-out rate into consideration, sample size will be 48 per group (total sample size: 192 subjects).

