4.3 Sample Size

Sample size was estimated based on the previous global Phase 2 trial (Study M13-537). Assuming an ACR20 response rate of 46% for placebo group, 62% for low dose group (7.5 mg QD), 68% for middle dose group (15 mg QD) and 80% for high dose group (30 mg QD) of Upadacitinib, the sample size to have 90% power and two-sided alpha of 5% to detect a statistically significant dose-response using Cochran-Armitage test will be 42 subjects per group. And the sample size to demonstrate the superiority of Upadacitinib compared to placebo will be 46 subjects to provide the 90% power and 5% of two-sided alpha. Taking 5% of drop-out rate into consideration, sample size will be 48 per group (total sample size: 192 subjects).

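### The superiority sample size of 46 per group holds for 30 mg only, and no single dose, not even 30 mg, can receive an error-controlled superiority claim

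*SAP*

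**What the plan says.** - **Aim.** Protocol 5.6.1: "Period 1 is designed to test superiority of" "upadacitinib versus placebo for achieving the primary endpoint (ACR20) at Week 12". Period 1 objective 1 (protocol 4.0) puts confirmation of dose response first and the comparison with placebo second.
- **Sample size.** Protocol 8.2 gives two requirements. For the trend, the number "to detect a statistically significant dose-response using Cochran-Armitage test will be 42 subjects per group". For the comparison with placebo, "the sample size to demonstrate the superiority of upadacitinib compared to placebo will be 46 subjects to provide the 90% power". SAP 4.3 repeats the latter: "the sample size to demonstrate the superiority of Upadacitinib compared to placebo will be 46 subjects to provide the 90% power". Neither names a dose. The larger figure, with 5% drop-out, leads to 48 per group and 192 in total.
- **Error control.** SAP 9.2.5: "Multiplicity on the primary endpoint is controlled via using the Cochran-Armitage test across the multiple doses". Protocol 8.1.4.1.4 has the same rule and adds: "Nominal pairwise comparison of each upadacitinib dose to placebo is also performed as supportive information". Protocol 8.1.4.1.1 also calls the ACR20 pairwise tests nominal. The synopsis refers to "All nominal statistical comparisons of upadacitinib versus placebo for the primary and key secondary endpoints and for the three doses" and runs each at two-sided 0.05.
- **A looser SAP description.** SAP 9.2.1 lists the pairwise p-values within the primary analysis without calling them nominal, and SAP 9.1.1 promises formal inference for Period 1.

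**The concern.** The aim, the sizing and the error-control rule do not match. The design text promises superiority, and a superiority calculation sets the trial size, yet the multiplicity sections give no dose-placebo comparison confirmatory standing. A decisive 30 mg result would stay supportive.

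The 90% power is also attached to upadacitinib without qualification, so it can be read as covering all three doses. If it covers only 30 mg, a non-significant 15 mg or 7.5 mg result is quite likely even when the planning assumptions are true, and could be misread as lack of effect.

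**Working it through.** **Inputs** (protocol 8.2, SAP 4.3): ACR20 46% on placebo, 62% on 7.5 mg, 68% on 15 mg, 80% on 30 mg; two-sided 5%; 90% power; 48 per group. The three placebo groups of 16 are combined (protocol 8.1.4.1).

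**1. Reproduce the trend figure.** With centred scores c = −1.5, −0.5, 0.5, 1.5, mean rate p̄ = 0.64 and Σcp = 0.54:

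n = {1.96√[p̄(1−p̄)Σc²] + 1.2816√[Σc²p(1−p)]}² / (Σcp)² = (2.1037 + 1.3020)² / 0.2916 = 39.8.

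The continuity correction, (n/4){1 + √[1 + 2/(0.54n)]}², gives 41.6, so 42 as stated. The plan therefore appears to use continuity-corrected formulas.

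**2. Reproduce the superiority figure.** With d = p₁ − p₀ and p̄ the mean of the two rates:

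n = {1.96√[2p̄(1−p̄)] + 1.2816√[p₀(1−p₀) + p₁(1−p₁)]}² / d²

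n_cc = (n/4){1 + √[1 + 4/(nd)]}²

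- 30 mg: (1.3382 + 0.8190)² / 0.34² = 40.3; corrected 45.95, so **46**.
- 15 mg: (1.3723 + 0.8748)² / 0.22² = 104.3; corrected 113.2, so **114**.
- 7.5 mg: (1.3815 + 0.8916)² / 0.16² = 201.8; corrected 214.1, so **215**.

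Only 30 mg gives 46. Pooling the doses (mean 70%) against placebo at 3:1 needs 57 placebo subjects, so 46 is not a pooled calculation either.

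**3. Power at 48 per group.** Uncorrected power is Φ{(d√48 − 1.96√[2p̄(1−p̄)]) / √[p₀(1−p₀) + p₁(1−p₁)]}:

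- 30 mg: (2.3556 − 1.3382)/0.6391 = 1.59, so 94%.
- 15 mg: (1.5242 − 1.3723)/0.6826 = 0.22, so 59%.
- 7.5 mg: (1.1085 − 1.3815)/0.6957 = −0.39, so 35%.

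On the continuity-corrected basis, replace 48 by 48{1 − 1/(48d)}² = 42.3, 39.3 and 36.3. The results are 91%, 50% and 27%. The planned CMH test is closer to the uncorrected figures.

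**4. What the superiority sizing adds.** The trend alone needs 42/0.95 = 44.2, so 44 or 45 per group. The other 3 or 4 per group, 12 to 16 of the 192 patients, are there for the superiority comparison.

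**5. A trend-gated fixed sequence, by simulation.** Test the trend, then 30, 15 and 7.5 mg, each at two-sided 0.05 in the favourable direction, at planning rates with 48 per group. The trend succeeds in 94.7% of trials. Controlled claims follow with probability 93%, 58% and 29% (91%, 50% and 21% with continuity-corrected pairwise tests). The planned CMH test, with assumed strata of 10 and 38 per arm and no stratum effect, gives the same 93%, 58% and 29%.

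**6. What the trend says about lower doses, by simulation.** If only 30 mg works (46/46/46/80), the trend is still positive in about 91% of trials. Each lower dose then shows nominal superiority beside a positive trend in about 2.5% to 2.6% of trials, and at least one of the two in 4.6%. Under the fixed sequence, a false lower-dose claim occurs in 2.6%.

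**The case against.** The sentence in SAP 9.2.5 is true for what it claims: one trend test on one endpoint at 5% controls error for the dose-response hypothesis. The nominal status of the pairwise tests is stated in the synopsis, in protocol 8.1.4.1.1 and 8.1.4.1.4 and in SAP 9.2.5. Protocol 5.6.1 speaks of the drug, not of each dose, and a single confirmatory trend test is a recognisable choice for a Phase 2b/3 study. The planning rates rise with dose, and protocol 5.6.4 expects near-maximal effect at the exposure matched to 15 mg and a plateau at that matched to 30 mg. If response does not fall with dose, a significant trend already points to 30 mg. The gain from a formal 30 mg test is then mainly one of status: 93% against 94.7% for the trend. Formal tests of 15 and 7.5 mg would also fail often.

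Most of this stands, and it limits the point. It does not remove it. Increasing response is a planning premise, not a stated analysis assumption, and even with it a positive trend does not establish a lower dose. Disclosure in the multiplicity sections does not repair the sample-size text, which states 90% power for superiority and leaves the reader to find out that this applies to one dose of three.

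A reader might go further and infer hidden alpha inflation. The documents do not support that: nothing beyond the trend is claimed as controlled. Counting significant differences in either direction, the chance that a lower dose is significant beside a significant trend when only 30 mg works is 7.2%. That count includes results favouring placebo; the superiority figure is 4.6%.

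**Conclusion.** The point holds as a mismatch between stated aim, sizing and error control, with modest consequences. The figure of 46 is correct arithmetic for 30 mg versus placebo and should say so; it should not be read as an error or as evidence that the trial is too small for its trend test. Superiority power at 48 per group is about 94%, 59% and 35% for 30, 15 and 7.5 mg (91%, 50% and 27% continuity-corrected). Under the present rule no individual dose can receive a controlled superiority claim, including the comparison that sets the trial size.

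This rests on the plan's assumed response rates, 48 analysed per group, trend scores 0 to 3, and no effect of prior bDMARD use on response, since the documents give no rates by stratum. The reproduction of 42 and 46 makes the continuity-corrected convention very likely, but the documents do not name the method.

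**What to change.** 1. **In any case, protocol 8.2 and SAP 4.3.** State that 46 per group gives 90% power for 30 mg versus placebo only, and give the power at 48 per group for 15 mg and 7.5 mg with the method used.
2. **If Week 12 is not yet unblinded, SAP 9.2.5 and protocol 8.1.4.1.4.** Add: *If the trend test is significant at two-sided 0.05 in the favourable direction, 30 mg, then 15 mg, then 7.5 mg will be tested against combined placebo on Week 12 ACR20 with the planned CMH test, each at two-sided 0.05, stopping at the first non-significant result. All other comparisons are nominal.* Protocol 8.1.4.1.1, the synopsis and SAP 9.2.1 need matching edits; otherwise the protocol would still call these tests nominal.
3. **If Week 12 is already unblinded, or the sponsor keeps the trend as its only confirmatory test.** Make change 1, align protocol 5.6.1 with the nominal status of the pairwise tests, and report any sequence as post hoc. The documents do not settle which case applies: the SAP is dated 31 August 2017 and the protocol synopsis 23 February 2018.

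The cost is wording in both documents, so a protocol amendment as well as a SAP revision, with no patients and no alpha. Under change 2 a lower dose has no formal claim once a higher dose fails, but it has none now. The 15 mg and 7.5 mg tests would be underpowered, and the text should say that failure there is not evidence of no effect.

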9.2.6 Efficacy Subgroup Analysis

The primary efficacy endpoint will be examined in the subgroups listed in [Table 8](#) below. Treatment difference between each Upadacitinib dose and the combined placebo group will be presented with point estimate and 95% confidence interval using normal approximation. No p-value will be provided for subgroup analysis. If any of the resulting subgroups has fewer than 10% of the planned study size (i.e., < 20 subjects), the subgroup analyses for that variable will not be presented.

Table 8. Subgroups for Efficacy Analysis

Subgroup Factor	Categories
Age	< 40, (40, 65), ≥ 65
Sex	Male or Female
Weight	< 60 kg or ≥ 60 kg and < 45 kg, (45, 60), > 60 kg
BMI	< 25 or ≥ 25
Duration of RA diagnosis	< 5 year or ≥ 5 year
Baseline Rheumatoid Factor Status	Positive or Negative
Baseline Anti-CCP Antibody Status	Positive or Negative
Baseline both RF positive and Anti-CCP positive	Yes or No
Baseline DAS28 [hsCRP]	≤ 5.1 or > 5.1
Prior bDMARD use	Yes or No

9.2.7 Summary of Efficacy Analysis for Period 1

Table 9 below provides the overview of the efficacy analyses for Period 1 to be performed on different endpoints.

Table 9. Summary of Efficacy Variables and Corresponding Analyses for Efficacy Analysis in Period 1

Efficacy Variables	Analysis Method
Primary Variables	
• ACR20 response at Week 12	
 The dose-response curve will be shown graphically with CI for each dose and Cochran-Armitage test will be conducted. Point estimate and 95% CI of the response rate for each Upadacitinib dose group and the combined placebo group. The 95% CI will be based on normal approximation. Point estimate, 95% CI and p-value for the treatment comparison between each Upadacitinib dose group and the combined placebo group, where the p-value is constructed using the Cochran-Mantel-Haenszel test adjusting for stratification factor prior bDMARD use. The 95% CI will be based on normal approximation. Subgroup analysis. Imputation: NRI for primary analysis and OC for sensitivity analysis Analysis Set: FAS and Per Protocol Analysis Set as supportive analysis (NRI only).
Key Secondary Variables	
Binary Endpoints: 
 ACR50/70 response at Week 12 ACR20 response at Week 1 Proportion of subjects achieving LDA based on DAS28 (CRP) at Week 12 Proportion of subjects achieving Clinical remission (CR) based on DAS28 (CRP) at Week 12 	
 Point estimate and 95% CI of the response rate for each treatment group. The 95% CI will be based on normal approximation. Point estimate, 95% CI and p-value for the treatment comparison between each Upadacitinib dose group and the combined placebo group using the Cochran-Mantel-Haenszel test adjusting for stratification factor prior bDMARD use. The 95% CI will be based on normal approximation. Imputation: NRI for primary analysis and OC for sensitivity analysis Analysis Set: FAS

Table 9. Summary of Efficacy Variables and Corresponding Analyses for Efficacy Analysis in Period 1 (Continued)

Efficacy Variables	Analysis Method
Key Secondary Variables (continued)	
Continuous Endpoints: 
 Change from baseline in DAS28 (CRP) at Week 12 Change from baseline in HAQ-DI at Week 12 Change from baseline in SF-36 Physical Component Score (PCS) at Week 12 Change from baseline in FACIT-F Change from baseline in RA-WIS Change from baseline in morning stiffness (severity). 	
 LS mean, and 95% CI within each treatment group and LS mean, 95% CI and p-values between each Upadacitinib dose group and the combined placebo group using ANCOVA model with treatment, prior bDMARD use and baseline value as covariates. Imputation: MI Analysis Set: FAS LS mean and 95% CI within each treatment group and LS mean, 95% CI and p-values between each Upadacitinib dose group and the combined placebo group using MMRM model with fixed effects of treatment, visit and treatment-by-visit interaction, prior bDMARD use and baseline value as covariate. Analysis Set: FAS
Additional Variables (Summarized at all Visits up to Week 12)	
Binary Endpoints: 
 ACR20/50/70 response rate Proportion of subjects achieving LDA and CR based on DAS28 (CRP), DAS28 (ESR), SDAI, and CDAI criteria 	
 Point estimate and 95% CI of the response rate for each treatment group. The 95% CI will be based on normal approximation. Point estimate, 95% CI and p-value for the treatment comparison between each Upadacitinib dose group and the combined placebo group using the Cochran-Mantel-Haenszel test adjusting for stratification factor prior bDMARD use. Nominal p-value will be provided, and the 95% CI will be based on normal approximation. Imputation: NRI for primary analysis and OC for sensitivity analysis Analysis Set: FAS

Table 9. Summary of Efficacy Variables and Corresponding Analyses for Efficacy Analysis in Period 1 (Continued)

Efficacy Variables	Analysis Method
Additional Variables (Summarized at all Visits up to Week 12) (continued)	
Continuous Endpoints: 
 Change from baseline in individual components of ACR response Change from baseline in DAS28 (CRP) and DAS28 (ESR) Change from baseline in morning stiffness (severity and duration) Change from baseline in EQ-5D-5L Change from baseline in SF-36 Change from baseline in FACIT-F Change from baseline in RA-WIS 	
 LS mean and 95% CI within each treatment group and LS mean, 95% CI and p-values between each Upadacitinib dose group and the combined placebo group using MMRM model with fixed effects of treatment, visit and treatment-by-visit interaction, prior bDMARD use and baseline value as covariate. Analysis Set: FAS

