9.3 Long Term Efficacy Analysis

Assessments to evaluate long term efficacy will be analyzed for the following measures at Week 1, 2, 4, 8, 12, 16, 20, 24, 36, 48, and every 12 weeks thereafter until completion of the study.

- ACR20/50/70 response rates;
- Change from baseline in individual components of ACR response;
- Change from baseline in DAS28 (CRP);
- Change from baseline in DAS28 (ESR);
- Change from baseline in morning stiffness (severity and duration);
- Proportion of subjects achieving LDA and proportion of subjects achieving CR based on DAS28 (CRP), DAS28 (ESR), SDAI, and CDAI criteria;
- Proportion of subjects with no concomitant corticosteroid use (among subjects with corticosteroid use at baseline).

Assessments to evaluate long term efficacy will be analyzed for the following measures at Week 4, 12, 24, 48:

- Change from baseline in EQ-5D-5L;
- Change from baseline in FACIT-F;
- Change from baseline in RA-WIS.
- Change from baseline in SF-36.

Descriptive statistics will be provided for each randomized treatment group sequence as defined in Section 9.1.1. These include the number of observations, mean, standard deviation, 95% CI, median, minimum, Q1, Q3 and maximum for continuous endpoints; and frequencies and percentages with 95% CI using normal approximation for binary endpoints. Plot for each randomized treatment group sequence over time will be provided up to Week 36 and 48.

No missing data imputation will be applied. All efficacy analyses will be based on As Observed (AO) analysis.

Table 10 below provides the overview of the long term efficacy analyses to be performed on different endpoints.

Table 10. Summary of Efficacy Variables and Corresponding Analyses for Long Term Efficacy Analysis

Efficacy Variables	Analysis Method
Binary Endpoints:	

 • ACR20/50/70 response by visit • LDA and CR based on DAS28 (CRP), DAS28 (ESR), SDAI, and CDAI criteria by visit • Proportion of subjects with no concomitant corticosteroid use (among subjects with corticosteroid use at baseline) 	
 • Point estimate and 95% CI of the response rate for each randomized treatment group sequence • Plot for each randomized treatment group sequence over time • Imputation: AO • Analysis Set: FAS
Continuous Endpoints:	

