10.2.2.1 Adverse Events Overview

The number and percentage of subjects experiencing TEAEs will be summarized by "as treated" treatment group and overall for the following AE categories.

- All TEAEs
- Treatment-emergent serious adverse events (SAEs)
- Treatment-emergent severe adverse events
- TEAEs reasonably possibly related to study drug
- TEAEs of special interest
- TEAEs leading to discontinuation of study drug
- TEAE leading to death

Additional AEs may be considered for tabulation/summary based on recommendations from Clinical and Safety as deemed appropriate.

For TEAEs of special interest, the point estimate and 95% CI (using normal approximation) will be provided for the treatment difference in AE percentage between each Upadacitinib dose group and the combined placebo group.

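### Normal-approximation 95% intervals for single-group response rates fall short of 95% coverage in the 16-subject long-term sequences and at rates near 0 or 1, and the SAP names no small-count alternative (minor)

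*SAP*

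**What the plan says.** The SAP uses one interval method for all binary results.

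- **Primary endpoint, single rates (SAP 9.2.1):** "Point estimate and 95% CI using normal approximation will be provided for the response rate for each randomized treatment group".
- **Primary endpoint, comparisons (SAP 9.2.1):** "Point estimate, 95% CI using normal approximation and p-value for the treatment comparison will be presented".
- **Key secondary and additional binary endpoints (SAP 9.2.4 and Table 9):** "The 95% CI will be based on normal approximation". Subgroup differences in SAP 9.2.6 use the same method.
- **Long-term efficacy (SAP 9.3):** "frequencies and percentages with 95% CI using normal approximation for binary endpoints". Results are shown for six treatment sequences on As Observed data. SAP 4.2 gives the three placebo-to-upadacitinib sequences 16 subjects each.
- **Adverse events of special interest (SAP 10.2.2.1):** "the point estimate and 95% CI (using normal approximation) will be provided for the treatment difference in AE percentage".

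No score, exact or sparse-count interval appears anywhere.

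On stratification of the difference interval, Table 9 is not uniform. In the primary row the Cochran-Mantel-Haenszel (CMH) method is attached to the p-value alone: "where the p-value is constructed using the Cochran-Mantel-Haenszel test adjusting for stratification factor prior bDMARD use". In the key secondary row, one sentence covers the estimate, the interval and the p-value for each dose against the "combined placebo group using the Cochran-Mantel-Haenszel test adjusting for stratification factor prior bDMARD use". No variance formula is given in either row.

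**The concern.** The usual normal-approximation (Wald) interval takes its standard error from the observed proportion. That standard error shrinks to zero as the observed count approaches 0 or n. The interval can then run below 0% or above 100%, or collapse to a point, and its true coverage can be well under the label. The plan applies it to groups of 16, and to endpoints such as ACR70, remission and Week 1 ACR20, where counts on placebo may be small. A table showing 0/48 with limits of 0% to 0%, or 16/16 with limits of 100% to 100%, overstates what is known. For safety differences, no events in either arm would give an interval of zero width around zero.

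Separately, a programmer cannot tell from the SAP whether the difference interval printed beside a CMH p-value is meant to be adjusted for prior bDMARD use.

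**Working it through.** **Inputs**

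- Group sizes: 48 per Period 1 group (placebo combined) and 16 per placebo-switch sequence (SAP 4.2).
- Rates: "Assuming an ACR20 response rate of 46% for placebo group, 62% for low dose group (7.5 mg QD), 68% for middle dose group", and 80% for 30 mg (SAP 4.3).
- Rates for ACR70, remission and Week 1 ACR20 are not in the documents. I take 2% to 20% as an assumed range.

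The plan gives no coverage figure beyond the nominal 95%. As a check on how its rates are meant, the 46 per group for superiority in SAP 4.3 reproduces for 80% against 46% with a continuity correction.

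**Formulas** (z = 1.96, p̂ = x/n)

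- Wald: p̂ ± z√(p̂(1−p̂)/n).
- Wilson: centre (p̂ + z²/2n)/(1 + z²/n), half-width z√(p̂(1−p̂)/n + z²/4n²)/(1 + z²/n).
- Exact coverage at true rate p: the sum of binomial probabilities of those x whose interval contains p.

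**Worked case 1: n = 16, p = 80%.** The Wald interval contains 80% only for x = 9 to 14 (x = 8 gives 25.5% to 74.5%; x = 15 gives 81.9% to 105.6%).

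- Coverage = 1 − P(x ≤ 8) − P(15) − P(16) = 1 − 0.0070 − 0.1126 − 0.0281 = 0.852.
- The upper limit exceeds 100% for x = 13, 14 or 15: 0.2463 + 0.2111 + 0.1126 = 0.570.
- With 16/16, Wald gives 100% to 100%; Wilson gives 80.6% to 100%.

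**Worked case 2: n = 48, p = 2%.** The Wald interval contains 2% for x = 1 to 5.

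- P(0) = 0.98^48 = 0.379 and P(x ≥ 6) = 0.0004, so coverage = 0.620.
- With 0/48, Wald gives 0% to 0%; Wilson gives 0% to 7.4%.
- With 2/48, Wald gives −1.5% to 9.8%; Wilson gives 1.2% to 14.0%.

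**Single rates, n = 16, at the SAP's ACR20 rates for the three doses**

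| True rate | Wald coverage | Upper limit above 100% | Wilson coverage |
|---|---|---|---|
| 62% | 87.1% | 8.8% | 93.2% |
| 68% | 91.5% | 19.3% | 94.3% |
| 80% | 85.2% | 57.0% | 94.5% |

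**Single rates, n = 48, assumed low rates**

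| True rate | Wald coverage | Negative lower limit | Zero width | Wilson coverage |
|---|---|---|---|---|
| 2% | 62.0% | 60.5% | 37.9% | 92.9% |
| 3% | 76.5% | 71.3% | 23.2% | 94.4% |
| 5% | 91.2% | 69.7% | 8.5% | 96.8% |
| 8% | 90.1% | 44.0% | 1.8% | 94.6% |
| 10% | 86.4% | 27.3% | 0.6% | 94.7% |
| 15% | 93.4% | 5.7% | 0.0% | 96.0% |
| 20% | 92.9% | 0.8% | 0.0% | 95.4% |

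**Single rates, n = 48, primary endpoint.** Wald coverage is 94.1% (46%), 94.2% (62%), 95.4% (68%) and 92.9% (80%).

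**Differences, 48 against 48, unstratified Wald.** Coverage is 94.4% (80% v 46%), 93.9% (62% v 46%), 94.5% (68% v 46%), 92.6% (20% v 2%), 94.5% (20% v 5%) and 94.4% (30% v 10%). It falls to 89.8% at 5% v 2%.

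**The case against.** The strongest reply is that nothing in the trial turns on these intervals. The primary inference is the Cochran-Armitage test. SAP 9.2.5 calls the pairwise comparisons nominal and supportive, and their p-values come from CMH. Long-term results are descriptive. A reader who sees 0/48 or 16/16 will not be misled about the data. All of this stands, and it is why the point is minor. It does not make an interval labelled 95% correct when its coverage is 85% at the plan's own rate.

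Three stronger readings are tempting and should be resisted.

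- **That the difference intervals are unstratified.** The SAP does not say so. The key secondary row of Table 9, and SAP 9.2.4, can be read as tying the interval to the CMH analysis, and a stratum-weighted difference with a large-sample variance is also a normal approximation. The supportable statement is that stratification is unclear.
- **That severe under-coverage is expected for placebo ACR70, remission or Week 1 ACR20.** The documents give no rates for these. The 62% figure belongs to an assumed 2%. At 15 to 20% the shortfall is about 2 points.
- **That all binary intervals are defective.** The primary ACR20 intervals, and the differences at 48 against 48 computed with an active rate of 20% or more, cover about 93 to 95%.

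It would also be wrong to promise that a better interval will agree with the CMH p-value. Enumerating 48 against 48 in a single stratum, the chance of disagreement at 0.05 is 2.6% for Wald and 2.9% for Newcombe at 20% v 2%, and 3.0% and 3.6% at 20% v 5%. Newcombe does better at 30% v 10% (2.6% against 0.2%).

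**Conclusion.** The point holds for single-group rates in small groups or near 0% and 100%. In the 16-subject sequences it follows from the SAP's own figures: coverage of 85 to 92% against 93 to 95% for Wilson, and a better-than-even chance of an impossible upper limit at an 80% rate. This assumes that switched subjects reach the Week 12 planning rates on active drug and that all 16 are observed; As Observed analysis can leave fewer.

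At 48 per group the size depends on assumed rates. It is severe at 2 to 3%, mostly moderate at 5 to 10%, and slight at 15 to 20%. For differences, the finding is mainly that the SAP leaves the formula and its stratification unclear.

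Reported precision is affected; the trial's primary conclusion is not. Severity: minor.

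**What to change.** - **Single-group response rates** (SAP 9.2.1, 9.2.3, 9.2.4, 9.3 and Tables 9 and 10): replace the normal approximation with Wilson intervals.
- **Treatment differences in Period 1 efficacy:** name one score-type interval, Newcombe or Miettinen-Nurminen, stratified by prior bDMARD use so that it matches the CMH adjustment. State it in the same words in every row of Table 9.
- **Subgroup differences (SAP 9.2.6) and differences for adverse events of special interest (SAP 10.2.2.1):** use the unstratified version of the same interval. Prior bDMARD use is itself one of the subgroups, so stratifying by it there would be empty.
- Add a sentence that the interval and the CMH p-value may occasionally disagree at 0.05.

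The cost is SAP wording and a programming option. No new data are needed, and the sample size and primary test are unchanged.
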